11.2. ADVERSE EVENTS – SEVERITY RATING

The severity of each AE should be characterized and then classified into one of three clearly defined categories as follows:

- Mild – the AE does not interfere in a significant manner with the subject's normal functioning level. It may be an annoyance.
- Moderate – the AE produces some impairment of functioning but is not hazardous to health. It is uncomfortable or an embarrassment.
- Severe – the AE produces significant impairment of functioning or incapacitation and is a definite hazard to the subject's health.

These three categories are based on the Investigator's clinical judgment, which in turn depends on consideration of various factors such as the subject's report and the physician's observations. The severity of the AE should be recorded in the appropriate section of the EDC.

11.3. ADVERSE EVENTS – RELATIONSHIP TO STUDY DRUG

The relationship of each AE to the study drug will be based on the Investigator's assessment as to whether there is a reasonable possibility the AE was caused by the study drug. This assessment will be based on the Investigator's clinical judgment, which in turn depends on consideration of various factors such as the subject's report, the timing of the AE in relationship to study drug administration/discontinuation, the Investigator's observations, and the Investigator's prior experience. The Investigator's assessment of the relationship of the AE to the study drug will be recorded in the appropriate section of the EDC.

11.4. SERIOUS ADVERSE EVENTS AND UNEXPECTED ADVERSE EVENTS – DEFINITIONS

A Serious Adverse Event (SAE) includes (but is not limited to) an experience occurring at any dose that results in any of the following outcomes:

- Death
- A life-threatening event (i.e., the subject is at immediate risk of death from the reaction as it occurs). "Life-threatening" does not include an event that, had it occurred in a more serious form, might have caused death. For example, drug-induced hepatitis that resolved without evidence of hepatic failure would not be considered life-threatening even though drug-induced hepatitis can be fatal.
- In-patient hospitalization (hospital admission, not an emergency room visit) or prolongation of existing hospitalization.
- A persistent or significant disability/incapacity (i.e., a substantial disruption of the subject's ability to carry out normal life functions).
- A congenital anomaly/birth defect.

In addition, medical and scientific judgment should be exercised in deciding whether other situations should be considered an SAE (i.e., important medical events that may not be immediately life-threatening or result in death but may jeopardize the subject or may require medical or surgical intervention to prevent one of the other outcomes listed in the definition above). Examples of such medical events include (but are not limited to): allergic bronchospasm requiring intensive treatment in an emergency room or at home, blood dyscrasias or convulsions that do not result in in-patient hospitalization, or the development of drug dependency or drug abuse.

An **unexpected** AE is one for which the specificity or severity is not consistent with the current Investigator's Brochure. For example, hepatic necrosis would be unexpected (by virtue of greater severity) if the Investigator's Brochure listed only elevated hepatic enzymes or hepatitis.

Similarly, cerebral thromboembolism and cerebral vasculitis would be unexpected (by virtue of greater specificity) if the Investigator's Brochure listed only cerebral vascular accidents.

11.5. SERIOUS ADVERSE EVENTS – REPORTING

The reporting of SAEs by the Sponsor to regulatory authorities (e.g., FDA) is a regulatory requirement. Each regulatory agency has established a timetable for reporting SAEs based upon established criteria. Likewise, it is the responsibility of the Principal Investigator to report SAEs to the IRB/EC.

All SAEs must be reported immediately (**within 24 h of learning of the event**) by e-mail to:

Premier Research Global Pharmacovigilance
[contact]

Do not delay reporting a suspected SAE to obtain additional information. Any additional information, if collected, can be reported to the Sponsor as a follow-up to the initial report.

Sites are to follow their IRB/EC requirements for reporting SAEs/AEs.

In the case of a death or other SAE that has occurred within 30 days after receiving study drug, the Principal Investigator must also report such an event within 24 hours of being notified. Your local IRB may also require these reports.

In the event of any SAE (other than death), the subject will be instructed to contact the study physician (Principal Investigator or designee) using the phone number provided in the

Informed Consent Form. All subjects experiencing an SAE will be seen by a Principal Investigator or designee as soon as feasible following the report of an SAE.

12. STATISTICAL CONSIDERATIONS

12.1. ANALYSIS POPULATION

The Safety Analysis Set includes all subjects who receive study treatment.

12.2. SAFETY ANALYSIS

Adverse events reported on CRFs will be mapped to preferred terms and organ systems using the MedDRA mapping system. Vital signs and clinical laboratory results will be descriptively summarized in terms of change from Study Day 1 values.

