Simufilam has been tested in single dose and repeat dose oral toxicity studies of up to 6 months in rats and 9 months in dogs. An initial 6-month repeat dose oral toxicity study in rats (with simufilam dosed at 50, 500 and 1000 mg/kg/day), indicated a toxicological response characterized by decreased body weights and adverse structural and functional alterations in the liver at 500 and 1000 mg/kg/day, including increased hepatic weight, hepatocellular hypertrophy and vacuolation, single/multiple basophilic/ eosinophilic/clear cell focus, hepatocellular degeneration, pigmentation, and oval cell hyperplasia. The presence of bile pigment was consistent with cholestasis. These findings correlated with changes to the clinical chemistry profile, including increased ALP and total/direct bilirubin. A 1-month recovery period showed complete recovery of the hepatocellular degeneration and partial recovery of hepatocellular hypertrophy; other microscopic findings in the liver remained. The no observable effect level (NOAEL) in this 6-month study was 50 mg/kg/day, corresponding to a safety margin of 6- and 1.6-fold based on C_{max} and AUC over the 100 mg b.i.d. dose in human subjects. A second 6-month repeat dose oral toxicity study in rats with simufilam at 125 and 250 mg/kg/day determined the 6-month NOAEL in the rat to be < 125 mg/kg/day, based on hepatocellular vacuolation in both sexes and hepatocellular hypertrophy in females at 125 and 250 mg/kg. Additional studies are ongoing to evaluate whether these liver effects are rat specific.

A 9-month toxicity study in dogs, a NOAEL of simufilam at 75 mg/kg. The high dose of 200 mg/kg/day was decreased to 150 mg/kg/day after 1 month due to bodyweight loss considered unsustainable for a 9-month study. Clinical signs were slight hypoactivity and incidences of slight muscle fasciculations early in the study, and salivation. There were no pathology findings, but the high dose was considered adverse due to two unexplained

deaths. The 75 mg/kg/day NOAEL provides 38- and 19-fold safety margins based on C_{max} and AUC over the 100 mg b.i.d. dose in subjects.

A full battery of genotoxicity studies was conducted (*in vitro* bacterial Ames, *in vitro* chromosomal aberration, and *in vivo* rat micronucleus test) and there were no mutagenic or clastogenic responses.

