7.1.9. Stopping Criteria

Liver chemistry threshold stopping criteria have been designed to ensure subject safety and to evaluate liver event etiology during administration of study drug. Potential discontinuation of study drug for abnormal liver function tests should be considered by the Investigator in consultation with the designated medical monitor if the study subject meets one or more of the following criteria:

- ALT or AST $\geq 4x$ ULN;
- ALT or AST $\geq 3x$ ULN and total bilirubin $\geq 2x$ ULN;
- ALT or AST $\geq 3x$ ULN if associated with the appearance or worsening of fatigue, nausea, vomiting, right upper quadrant pain or tenderness, fever, rash and/or eosinophilia; or
- ALP elevations, if deemed of liver origin and drug-related as follows:
 - ALP $> 3x$ ULN;
 - ALP $> 2.5x$ ULN and total bilirubin $> 2x$ ULN; or
 - ALP $> 2.5x$ ULN if associated with the appearance or worsening of fatigue, nausea, vomiting, right upper quadrant pain or tenderness, fever, rash and/or eosinophilia.

In the event of discontinuation due to abnormal liver function tests, the subject will be appropriately investigated to determine the potential cause and referred to a physician experienced in the treatment of hepatic disorders.

Study drug should be discontinued if a subject: (1) positively affirms suicidal ideation in response to questions number 4 or 5 in the suicidal ideation section of the C-SSRS, or (2) reports any suicidal behavior or non-suicidal self-injurious behavior since their last visit in response to the C-SSRS Suicidal Behavior questions. The subject should be referred to a psychiatrist or an appropriate health care professional for further evaluation and

management.

Bodyweight loss of ≥ 2 kg from Study Day 1 resulting in a BMI < 18.5 is an additional stopping criterion. (Note: BMI at any specific visit utilizes the height and weight recorded on that day.)

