#### 9.1.4. Summaries of Adverse Events

An overall summary of TEAEs will be provided by treatment. This summary will present number and percentage of participants with TEAEs per the following classifications:

- Participants with any TEAEs
- Participants with Treatment-Emergent Drug-Related AEs
- Participants with Treatment-Emergent AEs by Maximum Severity as Mild, Moderate, and Severe.
- Participants with TEAE leading to discontinuation from study
- Participants with Treatment-Emergent SAEs
- Participants with Treatment-Emergent SAEs leading to discontinuation from study
- Participants with Treatment-Emergent SAEs resulting in death

The following summary tables for TEAEs will be presented:

- Number and percent of participants reporting treatment-emergent AEs, grouped by MedDRA system organ class and preferred term
- Number and percent of participants reporting treatment-emergent drug-related AEs, grouped by MedDRA system organ class, and preferred term
- Number and percent of participants reporting treatment-emergent AEs, grouped by MedDRA system organ class, preferred term, and maximum severity
- Number and percent of participants reporting treatment-emergent SAEs will be tabulated by system organ class and preferred term and presented by treatment.
- Number and percent of participants reporting treatment-emergent AEs leading to study discontinuation, grouped by MedDRA system organ class and preferred term

For the summary tables above, the SOC terms and PTs will be presented in decreasing order of the total number of participants (frequency) who experienced each AE. System organ class terms and PTs with the same frequency will be presented alphabetically. In the case of multiple occurrences of the same TEAE within the same participant, each participant will only be counted once for each preferred term.

The following data listings for AEs will be provided for each participant by displaying the events captured on the CRF:

- All AEs,
- All serious AEs,
- All AEs leading to study discontinuation, and
- All AEs leading to Death.

In the AE data listings, all AEs will be displayed. AEs that are not treatment-emergent will be flagged in the AE listings.

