# 10. Changes from Planned Analyses

Due to the early sponsor termination of PTI-125-10, the following analyses will no longer be tabulated/listed:

- Mean change in clinical laboratory values from baseline to Weeks 4, 28 and 52
- Mean change in vital signs (blood pressure [supine], temperature, pulse rate) from baseline to Weeks 4, 16, 28, 40, and 52
- Mean change in body weight from baseline to Weeks 4, 16, 28, 40, and 52

- Shifts in physical exam (PE) findings from baseline to Weeks 4, 16, 28, 40, and 52
- Shifts in neurological exam (NE) findings from baseline to Week 4, 16, 28, 40, and 52
- Mean change in ECG parameters from baseline to Weeks 4, 28, and 52
- Concomitant medications/treatments usage
- Shifts in the C-SSRS from baseline to Weeks 4, 16, 28, 40, and 52.
- Shifts in HbA1c values from baseline to Weeks 28 and Week 52. The analysis is done separately among subjects who were previously on placebo and simufilam in PTI-125-06 and PTI-125-07 phase 3 studies.

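### No planned output counts the subjects who met the protocol's own liver, weight/BMI or suicidality thresholds, and the final SAP removes the underlying results from tables and listings

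*Protocol*

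**What the plan says.** Protocol 7.1.9 states the purpose of the liver rules: "Liver chemistry threshold stopping criteria have been designed to ensure subject safety and to evaluate liver event etiology during administration of study drug". The rules are multiples of ULN for ALT or AST and for ALP, used alone, together with bilirubin, or together with symptoms. Meeting one does not by itself stop treatment: "Potential discontinuation of study drug for abnormal liver function tests should be considered by the Investigator in consultation with the designated medical monitor". The same section has a weight rule (a loss of at least 2 kg from Study Day 1, "resulting in a BMI < 18.5 is an additional stopping criterion"). It also has a suicidality rule, met when a subject "positively affirms suicidal ideation in response to questions number 4 or 5 in the suicidal ideation section of the C-SSRS" or reports suicidal or self-injurious behaviour.

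On analysis, Protocol 12.2 says: "Vital signs and clinical laboratory results will be descriptively summarized in terms of change from Study Day 1 values". SAP 10 lists what had been planned and is now withdrawn because the sponsor ended the study early. The list includes "Mean change in clinical laboratory values from baseline to Weeks 4, 28 and 52", the matching mean change in body weight, and shifts in C-SSRS. Neither tables nor listings of these will be made.

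What remains is adverse-event output. SAP 9.1.4 says: "An overall summary of TEAEs will be provided by treatment", followed by tables by organ class and preferred term. SAP 9, however, also promises that every item of safety and tolerability data will be listed.

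**The concern.** The primary objective is long-term safety. The protocol's toxicology section reports, in rats, "adverse structural and functional alterations in the liver at 500 and 1000 mg/kg/day", with raised ALP and bilirubin, and gives a 1.6-fold AUC margin at the rat NOAEL of 50 mg/kg/day. It also reports body-weight loss in rats and dogs. The protocol responds with thresholds for individual subjects. The natural summary of such a rule is the number of subjects who met it, and that number is planned nowhere.

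Without it, the report cannot state how many participants met the study's own liver criteria, or how many had transaminase and bilirubin elevation together. A reader also could not tell a true zero from a result that was never tabulated.

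**Working it through.** The documents give no figure on this point to reproduce. The check compares each threshold with the planned outputs and then sizes the missing count.

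**1. Thresholds against outputs** (Protocol 7.1.9 and 12.2; SAP 10 and SAP 12, Tables 3 and 4)

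| Criterion | Form before withdrawal (SAP 10) | Final SAP | Would restoring it give the count? |
|---|---|---|---|
| ALT/AST, bilirubin, ALP multiples | Mean change, Weeks 4, 28, 52 | Not tabulated, not listed | No |
| Weight loss with low BMI | Mean weight change, Weeks 4, 16, 28, 40, 52 | Not tabulated, not listed | No; no post-baseline BMI output is named |
| C-SSRS ideation 4-5 or behaviour | Shifts, same five visits | Not tabulated, not listed | Perhaps in part; shift categories are not stated |

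SAP Table 3 holds six AE summary tables and three AE listings. Table 4 holds three listings: disposition, demographics and TEAEs. None refers to a 7.1.9 criterion.

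**2. What the default statistics would show.** SAP 4.1 summarises continuous data by n, mean, SD, median, minimum and maximum. A visit maximum for ALT of 4 x ULN fits one subject at that level or five. The ALT maximum and the bilirubin maximum come from separate rows and may belong to different people, so joint elevation cannot be recovered.

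**3. What the AE tables would show.** Under Protocol 11.1 a new laboratory abnormality is an AE when it is clinically significant, which is a judgement. The SAP tables then carry organ class, preferred term, severity, relatedness and seriousness, but no multiple of ULN and no concurrent bilirubin. A liver criterion only prompts consideration of stopping drug, Protocol 7.1.8 allows drug to be restarted, and the SAP tabulates AEs leading to *study* discontinuation. A subject who crossed a threshold and stayed on study is absent from that table.

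**4. Conflict inside the SAP.** SAP 9 promises listings of all safety data, and SAP 12.3 says that in general there will be one listing per CRF domain. SAP 6.1.6 says data not analysed under the plan will appear in no table or listing, SAP 10 withdraws these domains, and Table 4 omits them.

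**5. Size of the missing statement.** N = 1,081 (SAP 3.3), assuming every subject has a post-first-dose value. The case counts k are assumed. Exact limits: lower = Beta(0.025; k, N − k + 1); upper = Beta(0.975; k + 1, N − k).

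| k | k/N | Exact 95% CI |
|---|---|---|
| 1 | 1/1,081 = 0.09% | 0.00% to 0.51% |
| 3 | 3/1,081 = 0.28% | 0.06% to 0.81% |
| 5 | 5/1,081 = 0.46% | 0.15% to 1.08% |
| 10 | 10/1,081 = 0.93% | 0.44% to 1.70% |

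For k = 0 the two-sided 95% upper limit is 1 − 0.025^(1/1,081) = 0.34%. The one-sided 95% limit is 1 − 0.05^(1/1,081) = 0.28%.

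The chance of seeing at least one case is 1 − (1 − p)^1,081. For assumed true rates of 0.1%, 0.2% and 0.5% it is 66%, 89% and 99.6%. The study is large enough for the count to be informative.

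**The case against.** The other side has several fair points.

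- **Protocol 12.2 does not exclude categorical summaries.** True: it says neither mean nor only, and SAP 10 shows that shifts had been planned for C-SSRS and HbA1c. For liver chemistry and weight, though, SAP 10 records mean change.
- **Other routes exist.** A DSMB reviews safety with its own outputs, which the SAP does not describe. The weight and C-SSRS rules are firmer than the liver rule, so those cases may surface in disposition by reason or in the AE discontinuation table. This stands as mitigation, but no route is tied to a criterion, and the liver rule is the weakest link.
- **The toxicology is mixed.** The dog study had no pathology findings and a 19-fold AUC margin, and work on rat specificity continues. That bears on how likely a liver signal is. It does not affect whether the protocol's own thresholds should be counted.
- **Some criteria cannot be programmed from numbers alone.** ALP needs a judgement on hepatic origin and drug cause, and two lines need linked symptoms. This stands, and the fix allows for it.

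A reader might infer that hepatic outliers are averaged away. The documents do not support that: the final SAP produces no mean to hide them, C-SSRS was never planned as a mean, and the default maximum would have shown the most extreme value at each visit. A reader might also infer that the trial cannot address long-term safety at all. That goes too far, given the AE tables and the DSMB.

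**Conclusion.** The point holds as an omission. Protocol 7.1.9 defines who crosses a threshold, and no planned output counts them. The final SAP removes the laboratory, weight and C-SSRS results from which the count would come, and contradicts its own statement on listings. Restoring the withdrawn laboratory and weight tables would not repair this; restored C-SSRS shifts might help in part.

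The practical size is the statement the report cannot make, for example 0.46% (0.15% to 1.08%) with 5 cases, or at most 0.34% (two-sided) with none. These figures assume that all 1,081 subjects have a post-dose value; a smaller denominator widens them. They describe frequency only, since the study has no control arm. The change is worthwhile and cheap. The thresholds themselves are not in question.

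**What to change.** Amend SAP 9 and 12, and reconcile them with SAP 6.1.6 and 10.

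1. **One table**: n (%) with exact 95% CI of subjects meeting each criterion at any post-first-dose assessment, among those with at least one such value in that domain. Rows: each purely numeric ALT/AST criterion; ALT/AST with bilirubin; the numeric ALP multiples, alone and with bilirubin; the weight/BMI criterion; C-SSRS ideation 4-5; suicidal or self-injurious behaviour. State whether paired liver values must come from the same sample.
2. **One listing**: serial values, temporally associated AEs and study-drug status for each such subject. Enter subjects at the lowest multiples in 7.1.9 (ALT/AST 3 x ULN, ALP 2.5 x ULN), so that symptom-qualified cases and the judgement on ALP origin and drug cause can be read there.
3. **Two derivation rules**: the SAP cites protocol version 3.0 and a 52-week design, while the current protocol is open-ended, so say which visits count. SAP Table 1 records height on Study Day 1 only, while Protocol 7.1.9 uses same-day height, so say which height is used when none was taken.

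The assessments are scheduled from Week 4, so early termination does not itself prevent this. If the database is already locked, SAP 1 allows the outputs to be run and labelled as post hoc. The cost is one table, one listing and modest programming. No threshold or clinical rule changes.

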12.3. HbA1C ANALYSIS

HbA1c levels will be collected and measured repeatedly from all subjects for whom a Day 1 HbA1c has been collected (including re-entry subjects), and these data will be analyzed by a linear mixed model for repeated measurements. Two subject cohorts will be analyzed separately: those randomized to placebo in the PTI-125-06 or PTI-125-07 phase 3 studies, and those randomized to simufilam in those studies. The analytical model will be fully described in the statistical analysis plan.

12.4. PLASMA BIOMARKER ANALYSIS

Plasma assays may include P-tau217, glial fibrillary acidic protein, neurofilament light, and other biomarkers. All plasma biomarker data measured repeatedly will be analyzed by linear mixed models for repeated measurements. Subject cohorts of interest for separate analyses include subjects who participated in one of the plasma biomarker sub-studies of the PTI-125-06 or PTI-125-07 phase 3 studies; subjects randomized to placebo and subjects randomized to simufilam in the aforementioned studies. Within-subject change from baseline analyses may also be conducted. The analytical model and all other analyses will be fully described in the statistical analysis plan.

12.5. CLINICAL DEMENTIA RATING

CDR sum of boxes and/or global score assessments measured repeatedly will be analyzed using a linear mixed model for repeated measurements. Two subject cohorts will be analyzed separately: those randomized to placebo in the PTI-125-06 or PTI-125-07 phase 3 studies, and those randomized to simufilam in those studies. Within-subject change from baseline may also be conducted. The analytical model and all other analyses will be fully described in the statistical analysis plan.

12.6. INTERIM ANALYSIS

Interim analysis of plasma biomarker and cognitive data may occur at the discretion of the sponsor.

